Conventional physical rehabilitation (CPR) consists of traditional physical exercises that improve functional capacity (22,23). Over the past few years, it has been suggested that incorporating AVGs into CPR can optimize clinical and psychosocial outcomes in the elderly (24-26). AVGs have been reported to promote improvements in functional mobility, coordination, muscle strength, and cognitive function in older people (27-29). In addition, AVGs improve walking ability (30) and postural balance (31), as well as social well-being (perception of loneliness, social connectedness, and positive attitudes) (24). However, this research has focused on healthy elderly (30-33) and patients with neurocognitive pathologies (29,34-37). On the other hand, little information is available on older people with musculoskeletal conditions such as OA (38-40). In this regard, a systematic review conducted in patients with knee and/or hip OA indicates that the evidence is insufficient and inconclusive regarding the effectiveness of AVGs (38). Moreover, one study concludes that AVGs are a feasible and acceptable intervention for patients with knee OA (39). Interestingly, both studies raise the benefits and potential of AVGs in this population, urging further clinical trials (38,39).

3. RESEARCH QUESTION AND HYPOTHESIS.

- **Research question:** In older adults with knee and/or hip OA. Is AVG-guided physical exercise adjunct to CPR more effective than CPR alone in improving clinical and psychosocial outcomes?
- **Working hypothesis:** In older adults with knee and/or hip OA, AVG-guided physical exercise adjunct to CPR is more effective than CPR alone in improving clinical and psychosocial outcomes.

4. OBJECTIVES.

General objective: To determine the effects of an AVG-guided physical exercise program adjunct to CPR on clinical and psychosocial outcomes in older adults with knee and/or hip OA attended at a community-based family health center.

Specific objectives:

1. To characterize the study sample from sociodemographic, anthropometric, clinical, and psychosocial perspectives.
2. To compare the results of the primary outcome (functional mobility) and secondary outcomes between the study groups (experimental and control) in the different instances of outcome measurement.
3. To evaluate the clinical significance of the interventions and the clinical relevance of the interventions as perceived by the participants.

5. METHODS.

Study design and setting.

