The design is a two-arm parallel randomized clinical trial (RCT) and will be conducted according to the CONSORT statement. A control group (CG) will perform CPR, and an experimental group (EG) will perform AVG adjunct to CPR. Subjects will be invited to participate upon admission to the rehabilitation unit of a family health center. All study requirements will be explained, and all subjects will be required to sign an informed consent form.

Sample calculation.

The a priori calculated sample size using G*Power yielded 50 subjects. Statistical power $(1-\beta)=0.8$ and significance $(\alpha)=0.05$ were considered. In addition, a moderate effect size $(ES)=0.51$ was considered for the TUG test (functional mobility) to

detect a minimum clinically important difference (MCID) of 1.4 seconds. Ten subjects will be added for a potential dropout of 20%, finally estimating a sample of 60 subjects (CG=30; EG=30).

Participation criteria.

- Inclusion criteria: Age ≥ 60 and ≤ 84 years; Diagnosis of mild or moderate OA of the knee and/or hip; Independent walking capacity of at least 15 meters
- Exclusion criteria: Inability to interact with active video games; Undergoing treatment with opioids or other medications with a potential influence on the outcomes of interest; < 13 points in the abbreviated version of the Mini-Mental State Examination (MMSE-EFAM); OA associated with infectious, autoimmune, fractures or surgery; Participate or have participated in another physical-cognitive rehabilitation program during the last 3 months.

Randomization and allocation concealment.

A stratified randomization will be applied to balance the two study groups according to "age" (60-69, 70-79, 80-84 years) and "sex" (male, female). Allocation concealment will be ensured through sealed and consecutively numbered opaque envelopes.

Sample characterization.

Sociodemographic (age, sex, and education) and clinical characteristics (diagnosis of OA, comorbidity, history of falls, technical aids, and pharmacotherapy) will be collected by interview. In addition, height, body weight, and body mass index will be measured.

Study outcomes.

An experienced physical rehabilitation professional will perform the measurements in a blinded manner.

a) Primary outcome measure:

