- Pressure pain threshold. Wagner® FPX-25 algometer. It is expressed in kilogram/cm². Time Frame: Five-time points. Baseline (pre-intervention); at week 4 (after ten sessions from baseline); at week 7 (after 20 sessions from baseline); and week 10 (after 30 sessions from baseline). In addition, four weeks after the completion of the intervention.
- Health-related quality of life. SF-12v2 Chile-Spanish Questionnaire. Score from 0-100 points. Assessment of 8 dimensions (physical functioning [PF], role-physical [RP], bodily pain [BP], general health [GH], vitality [VT], social functioning [SF], role-emotional [RE], and mental health [MH]), and two summary scores (physical component summary [PCS] and mental component summary [MCS]). Time Frame: Three-time points. Baseline (pre-intervention); and week 10 (after 30 sessions from baseline). In addition, four weeks after the completion of the intervention.
- Adherence to treatment. Number of effective assistances at the end of treatment. A participant with an attendance $\geq 2/3$ of the total (30 sessions) is considered "adherent"

(≥ 20 sessions). Time Frame: One-time point. At week 10 (after 30 sessions from baseline).

- User satisfaction. The average score of 3 questions (overall level of satisfaction, expectation fulfillment, and recommendations to others) using a scale of 1 to 7 points, where 1 is the worst evaluation, and 7 is the best evaluation. Time Frame: Three-time points. At week 4 (after ten sessions from baseline); at week 7 (after 20 sessions from baseline); and week 10 (after 30 sessions from baseline).
- Therapeutic alliance. Subscale of the Pain Rehabilitation Expectations Scale (PRES). The score ranges from 1 to 44; a higher score is a higher therapeutic alliance. Time Frame: Three-time points. At week 4 (after ten sessions from baseline); at week 7 (after 20 sessions from baseline); and week 10 (after 30 sessions from baseline).

Interventions.

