The description of quantitative indicators (continuous or discrete) will be done using measures of central tendency (mean or median) and dispersion (standard deviation, interquartile ranges, and confidence intervals) according to their normality distribution. For the description of categorical variables (nominal and ordinal), absolute and relative frequency measures will be used. The R v.4.1.2 software will be used for the analyses ($p < 0.05$). The assumptions of normality and homoscedasticity will be verified using the Shapiro-Wilk and Levene tests, respectively. For variables that do not meet the assumption of normality, a two-step rank transformation will be applied. A two-way, repeated measures ANOVA will be used to determine intragroup and intergroup differences. Model effects are Group, Time, and their interaction over time (Group \times Time). Tukey's post hoc test will be used for variables with Group \times Time interaction. The statistical analyst will be blinded for the intervention groups, and in addition, an intention-to-treat analysis (multiple imputation method) will be considered for handling potential incomplete data. Clinical significance (ES) of interventions will be determined using Cohen's "d" (< 0.2 =negligible, $0.2-0.49$ =small, $0.5-0.79$ =moderate; ≥ 0.8 =large). Additionally, at the end of the intervention, patients will be asked to rate their overall change in clinical status (pain and functionality) using a 15-point scale. The global rating of change ranges from +7 ("a very great deal better") to 0 ("about the same") to -7 ("a very great deal worse"). The interpretation of changes is: 1-3 points=small, 4-5=moderate, and 6-7=large.

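### Randomisation is stratified by age band and sex but the analysis model omits both, so Group main effects and single-visit between-group comparisons are less efficient than they could be; a cheap improvement, not a validity problem

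*Combined protocol and SAP*

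**What the plan says.** Protocol section 5, under Randomization and allocation concealment: "A stratified randomization will be applied to balance the two study groups according to" age, in three bands (60-69, 70-79, 80-84), and sex. That makes six strata. Concealment by envelope is described. Whether allocation within a stratum is blocked, minimised or simple is not.

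The SAP specifies a two-way repeated-measures ANOVA: "Model effects are Group, Time, and their interaction over time". It names no covariate. Tukey's "post hoc test will be used for variables with Group" × Time interaction, so the pairwise comparisons are gated by that test. For missing data, "an intention-to-treat analysis (multiple imputation method) will be considered for handling potential incomplete data"; the variables in the imputation model are not listed.

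Three other places bear on the point:

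- Specific objective 2 compares outcomes "between the study groups (experimental and control) in the different instances of outcome measurement", which calls for between-group contrasts at individual visits.
- User satisfaction and therapeutic alliance have no baseline visit: "Three-time points. At week 4 (after ten sessions from baseline); at week 7" and week 10.
- Age and sex are collected anyway, under Sample characterization: "Sociodemographic (age, sex, and education) and clinical characteristics".

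**The concern.** The design balances the arms on age and sex, and the model then leaves whatever these factors explain in the error term. Two different things can follow, depending on a detail the protocol does not give.

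- **Restricted allocation within strata (for example, blocks).** The estimated group difference already benefits from the balance, but the unadjusted standard error does not reflect it. The reported standard error is too large and the test is conservative.
- **Simple randomisation within strata.** Little balance is guaranteed. The unadjusted test keeps its size, but the estimate is truly less precise than an adjusted one.

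The quantities exposed are the Group main effect and same-visit comparisons between arms. The Group main effect matters most for satisfaction and alliance. A group difference that is the same at weeks 4, 7 and 10 produces no Group × Time effect, so the Tukey gate would not open on it, and the Group main effect is then the SAP's between-group test. With 60 participants there is little precision to spare.

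**Working it through.** **Inputs from the documents.** Final N is 60 (30 per arm), with 50 before the dropout allowance; α = 0.05; target power 0.80; ES = 0.51 for TUG; MCID 1.4 s; six strata; five visits for most outcomes.

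**Assumptions, because the documents are silent.** R² is the share of single-visit outcome variance explained by age band and sex, taken as 0.1/0.2/0.3. ES 0.51 is read as a between-group Cohen's d, and tests are two-sided. The between-visit correlation is 0.7. Blocks are of 4. The sample mix is 45/40/15% by age band and 25% of one sex. Ten participants are lost at random and excluded; multiple imputation was not simulated. Data are normal.

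**The plan's own figure.** A two-sided two-sample t test at d = 0.51 needs 62 per arm (124 in total) for 80% power, so the stated 50 is not reproduced on this reading. That is a separate matter; the present point does not depend on it. The figures below use 25 per arm.

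**1. Single-visit comparison, formula.** In SD units, SE = √(2/25) = 0.283 unadjusted and √(2(1−R²)/25) adjusted. The ratio is 1/√(1−R²) = 1.05/1.12/1.20. Noncentral t power under exact balance is 0.424 unadjusted (48 df) and 0.460/0.505/0.559 adjusted (45 df).

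**2. Single-visit comparison, simulation (N = 60, 10 lost).**

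| Allocation within strata | Unadjusted type I error | Power, unadjusted | Power, adjusted |
|---|---|---|---|
| Blocks of 4 | 4.4/3.5/2.6% | about 42/41/41% | 46/50/55% |
| Simple | near 5% | about 42% | 43-44/47-48/52-53% |

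At R² = 0.05, power goes from 42.2% to 43.5% with blocks and from 42.0% to 41.5% with simple randomisation.

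**3. Where the loss sits.** With blocks and R² = 0.3, the reported unadjusted SE is 0.283, the estimate's true sampling SD is about 0.25, and the adjusted SE is 0.24. At R² = 0.1/0.2/0.3 the true SD of the unadjusted estimate exceeds the adjusted one by only 0.6/2.6/5.6%, while its reported SE is 4.5/11/19% larger. With simple randomisation the true precision loss is about 3/8/16%.

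**4. Group × Time.** A subject-level shift that is constant over visits cancels from every within-subject change. In a mixed model fitted to one simulated complete data set, the four interaction estimates and their standard errors agreed to five decimals with and without age and sex. Within-group visit contrasts are unaffected for the same reason.

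**5. Planned sequence (interaction gate, then week-10 comparison; blocks of 4; assumed effects 0, 0.17, 0.34, 0.51, 0.51).** The gate opens in about 60% of trials either way. The chance of passing it and then finding the difference depends on the Tukey family, which the SAP does not state:

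- Two groups within a visit: 29/30/29% unadjusted, 31/35/37% adjusted.
- All ten group-by-visit cells: 6/5/5% unadjusted, 7/8/10% adjusted.

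**6. Group main effect over weeks 4, 7 and 10 (constant d = 0.51).** The variance of a subject's mean is (1 + 2 × 0.7)/3 = 0.80, and removing R² leaves 0.70/0.60/0.50. Power by formula is 0.506 unadjusted and 0.559/0.625/0.704 adjusted. Simulation gives about 50% versus 55/62/70% with blocks and 52/58/67% with simple randomisation. The documents give no basis for R² on satisfaction or alliance.

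**7. If a baseline term were also in the model.** Residual variance is (1−R²)(1−r²), where r = (ρ−R²)/(1−R²) and ρ is the baseline correlation. At ρ = 0.7, power is 0.696 without age and sex and 0.703/0.714/0.729 with them. At ρ = 0.6 it is 0.598 versus 0.609/0.624/0.645. The gain is about nil to 5 points; with imperfect balance at ρ = 0.7 it was −0.2/0.5/2.0 points.

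**8. In seconds.** The sample size is meant to "detect a minimum clinically important difference (MCID) of 1.4 seconds". If ES 0.51 is a between-group d, SD = 1.4/0.51 = 2.75 s, and the single-visit 95% half-width is 2.011 × 2.745 × 0.2828 = 1.56 s unadjusted, against 1.48/1.40/1.31 s adjusted. The protocol states neither the metric nor an SD.

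**The case against.** The strongest reply is that the gatekeeping test is untouched, the unadjusted tests are valid, and the size of any gain rests on an R² that the documents do not give. All of that stands. At R² of 0.05 or less there is almost nothing to gain, and under simple randomisation adjustment can cost a little. The largest gains belong to satisfaction and alliance at R² = 0.3, which is an assumption only. The simulations also use normal data, whereas the SAP rank-transforms variables that are not normal. Under a ten-cell Tukey family, low power and the gate matter far more than the missing covariates.

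Four stronger readings are tempting, and the documents do not support them:

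- **That omitting stratification factors biases the comparison or inflates false positives.** It does neither; where size departs from 5%, it falls.
- **That precision is lost and the test is conservative, as two separate harms.** These are largely alternatives. Under restriction the fault is mainly the overstated standard error; under simple randomisation it is real imprecision.
- **That all the post hoc comparisons are affected.** The within-group visit contrasts are not; only same-visit comparisons between arms are.
- **That the TUG interval is known to be too wide by some number of seconds.** That needs ES 0.51 to be a between-group d, which is not stated, and the SAP does not specify an interval for the group difference.

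What survives is that passing the gate is not the final result. The same-visit contrast is what objective 2 asks for, and that contrast can be sharpened with data already in hand.

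**Conclusion.** The mismatch between design and model is plain in the current text, and its consequence is modest. To the extent that age or sex predicts an outcome, the Group main effect and single-visit between-group comparisons are less efficient than they need be, in the direction of missing an effect. At assumed R² of 0.1/0.2/0.3, single-visit power at d = 0.51 with 50 analysed would rise from about 42% to about 43-46/47-50/52-55%, the range within each pair covering simple and blocked allocation. The statement that Group × Time and within-group contrasts are unchanged rests on complete data and on age and sex effects that are constant over time. Severity is minor: a cheap improvement, not an error that invalidates the analysis.

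**What to change.** Add the age randomisation bands and sex as main-effect covariates in the repeated-measures models for the primary outcome and the repeatedly measured secondary outcomes. Where the two-step rank transformation is used, apply the covariates to the transformed response. Include both variables in the multiple-imputation model. Name the bands as the form of the age term, so that no choice is left for after the data are seen, and use main effects rather than six cells, because the 80-84 cells may be sparse. It would also help to state how allocation within strata is done, since that decides which of the two consequences applies.

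The cost is a sentence in the model text, one in the imputation text and about 3 degrees of freedom (two for age band, one for sex). If neither factor is prognostic, single-visit power falls by about 0.5 point with blocks of 4 (42.4% to 41.8%) and by about 2-3 points with simple randomisation within strata (41.9% to 39.1% in one set of runs). No new data are needed.

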Two experienced physiotherapists will perform the interventions. For both groups, the duration will be ten weeks with a frequency of 3 sessions per week (30 sessions). The intensity of the interventions in both groups will be controlled using a scale of 0 to 10 points, adjusting individually as "light" (effort < 5) and "moderate" (effort 5 to 6). For the progression of intensity, it is considered: i) Session 1 to 10 "light" 70% and "moderate" 30% of the session time; ii) Session 11 to 20 "light" 50% and "moderate" 50% of the session time; iii) Session 21 to 30 "light" 30% and "moderate" 70% of the session time. Adverse events, medications, and general health status will be monitored throughout the experimental period. The interventions are described below:

- Control Group (CG): Will receive a routine of four blocks of conventional exercises (50 minutes per session): Aerobic, muscle strengthening, postural balance, and flexibility. A warm-up phase will be performed before the exercise routine and a cool-down phase after the routine. In addition, before and after the session, physical agents will be applied in a standardized manner (electrotherapy and thermotherapy).
- Experimental group (EG): Will perform the same procedures as the CG, although the conventional exercise routine will last 30 minutes. Then, this group will perform an AVG intervention for 20 minutes so that the exercise time will be the same in both groups (50 minutes per session). The week before the interventions start, this group's participants will have a familiarization session with the AVGs. The AVG routine will be performed using a set of selected exercises and dynamic activities from the "Ring fit adventure" video game available for the Nintendo Switch® console.

REFERENCES.

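### The stated question is whether AVG added to CPR beats CPR alone, but the arms compare replacing 20 of 50 minutes of conventional exercise with AVG at equal total time

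*Combined protocol and SAP*

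**What the plan says.** Section 3 (Research question and hypothesis) asks: "Is AVG-guided physical exercise adjunct to CPR more effective than CPR alone in improving clinical and psychosocial outcomes". The working hypothesis states the same comparison as a claim of superiority: "AVG-guided physical exercise adjunct to CPR is more effective than CPR alone in improving clinical and psychosocial outcomes". The general objective in section 4 also calls the AVG programme an adjunct to CPR, without naming the comparator. Section 5, Study design and setting, describes the arms the same way: "A control group (CG) will perform CPR, and an experimental group (EG) will perform AVG adjunct to CPR".

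CPR is characterised in section 2: "Conventional physical rehabilitation (CPR) consists of traditional physical exercises that improve functional capacity". No duration is given there or in sections 3 and 4.

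Durations appear only in section 5, Interventions. Control group: "Will receive a routine of four blocks of conventional exercises (50 minutes per session". The experimental group follows the control group's procedures, "although the conventional exercise routine will last 30 minutes. Then, this group will perform an AVG intervention for 20 minutes". The reason given is to keep exercise time equal between the groups. The control routine also has a warm-up, a cool-down and physical agents before and after the session, and the experimental group keeps these.

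The contrast is nowhere described as replacement or substitution.

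**The concern.** Adjunct to CPR versus CPR alone is ordinarily read as the same CPR in both arms, with AVG on top in one. Under Interventions the experimental group gives up part of the conventional routine to make room for AVG. The hypothesis to be accepted or rejected is thus not the comparison that the randomisation delivers.

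What is at stake is interpretation. Suppose the groups do not differ. Judged against the stated hypothesis, that would be recorded as AVG failing to improve on CPR. It would fit equally well with AVG being as useful as the conventional exercise it displaced, which could be a helpful finding for a community centre. Suppose instead the experimental group does better. That supports exchanging some conventional exercise for AVG, whereas the hypothesis would lead a reader to conclude that AVG should be added to the usual routine.

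**Working it through.** **Inputs, all from section 5, Interventions.** Ten weeks at 3 sessions per week; control group 50 conventional minutes per session; experimental group 30 conventional plus 20 AVG minutes.

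**The plan's own figures reproduce.** 10 × 3 = 30 sessions. 30 + 20 = 50 minutes, equal to the control group's 50.

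**Exposure by arm**

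| | Control | Experimental | Difference |
|---|---|---|---|
| Conventional, per session | 50 min | 30 min | −20 min |
| AVG, per session | 0 | 20 min | +20 min |
| Conventional, 30 sessions | 30 × 50 = 1,500 min | 30 × 30 = 900 min | −600 min |
| AVG, 30 sessions | 0 | 30 × 20 = 600 min | +600 min |
| Total, 30 sessions | 1,500 min | 1,500 min | 0 |

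The reduction in the conventional exercise routine is 20/50 = 40%. Net exercise time added is zero, apart from one familiarisation session of unstated length that only the experimental group attends.

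**What each comparison estimates.** Let Y(c, a) be the mean improvement with c conventional and a AVG minutes per session.

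- Delivered contrast: D = Y(30, 20) − Y(50, 0).
- Add-on to the full routine: A = Y(50, 20) − Y(50, 0).
- Subtracting: A = D + [Y(50, 20) − Y(30, 20)].

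The bracket is what the removed 20 conventional minutes would contribute alongside AVG. No arm receives 50 + 20, so the trial has no data on it.

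- If D = 0, then A equals the bracket, which is unknown. A null result therefore does not imply A = 0.
- If D > 0, then A > 0 follows provided the bracket is not negative. That is plausible given section 2's statement that conventional exercise is beneficial, but it is an assumption the trial does not test.

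**The shorter-CPR reading gives no match either.** If CPR meant a 30-minute routine, the add-on contrast would be Y(30, 20) − Y(30, 0), and no arm receives 30 conventional minutes alone.

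**The analysis does not change this.** The SAP's repeated-measures ANOVA uses Group, Time and their interaction. Its group comparisons are between the arms as delivered, so they estimate D at each time point.

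**The case against.** The strongest reply is that nothing is hidden and little is wrong. Sections 3 and 4 attach no minutes to CPR, and section 2 speaks of building AVG into CPR, which fits AVG delivered inside a CPR session. Interventions then defines both arms exactly and gives the reason for the split. Read together, the plan compares CPR that includes AVG with CPR that does not, at equal exercise time. Matching time is also a sound choice: 20 minutes on top would give one arm more exercise and mix the effect of AVG with that of dose.

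Much of this stands. The time matching is deliberate, disclosed and legitimate, and the point does not criticise it. The looser reading of adjunct is possible, but it makes CPR mean 50 minutes in one arm and 30 in the other within a single comparison. Disclosure in Interventions does not alter the hypothesis against which the result will be judged.

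Three stronger readings are tempting and are not supported:

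- *The trial says nothing about adding AVG.* Too strong. If the removed minutes would help, or at least not harm, when given alongside AVG, a positive result bears indirectly on the add-on question.
- *The experimental group receives 40% less CPR.* The 40% applies to the conventional exercise routine only. Warm-up, cool-down, electrotherapy and thermotherapy are kept.
- *The replacement costs a calculable amount of Timed Up and Go effect and power.* The documents give 1.4 seconds as the minimum clinically important difference for the sample size. They do not say what 50 or 20 minutes of conventional exercise yields, nor that gain is proportional to time, so no figure can be derived.

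**Conclusion.** The point holds as a mismatch between the stated question and the delivered contrast. The trial estimates the effect of replacing 20 of 50 minutes of conventional exercise with AVG, which is 600 of 1,500 minutes over the programme, at equal total exercise time. The randomised comparison is valid for that question.

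A null result would not be evidence that AVG adds nothing to the full routine. A positive result would directly support the swap, and the add-on claim only with the extra assumption about the removed minutes.

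The exposure figures need only the stated minutes and full attendance at 30 sessions. The conclusion about the contrast rests on reading CPR as the routine the control group receives, which is the only CPR-alone condition in the plan. No effect on the size of the outcome or on power is claimed.

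It should be corrected because it changes what either result may be said to show.

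**What to change.** Reconcile sections 3 and 4 and the arm description under Study design and setting with Interventions. Which session content is intended is for the investigators to decide and state.

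If Interventions stands, reword the question, hypothesis, general objective and arm description along these lines: *CPR with part of the conventional exercise time replaced by AVG, versus CPR alone, at equal total exercise time*. Add one sentence saying that a null result is not evidence that adding AVG to the full routine has no benefit.

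In that case only wording changes; no procedure, sample size or analysis step moves. The price is a narrower claim than the present hypothesis makes.
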